### 1.2.2 Temozolomide

Temozolomide (TMZ) is an orally administered, second generation imidazotetrazine prodrug with essentially 100% oral bioavailability. TMZ spontaneously converts to the active alkylating agent 5-(3-methyltriazene-1-yl) imidazole-4-carboximide (MTIC) with extensive tissue distribution, including penetration of the blood-brain barrier and the cerebrospinal fluid. TMZ has notable antitumour activity against recurrent GBM (R08-1057), recurrent anaplastic astrocytoma, and advanced malignant melanoma, and other refractory cancers. TMZ has shown activity when added to radiotherapy for treatment of newly diagnosed GBM (R08-1056).

TMZ is rapidly absorbed and spontaneously converts to the active metabolite MTIC. Maximum plasma concentrations are observed 30 to 90 minutes after oral intake, and the plasma half-life is approximately 2 hours, with some delayed absorption when taken with food. Pharmacokinetics in the CSF compared with plasma showed an AUC of approximately 20% of the AUC. Patients usually tolerate TMZ well; mild to moderate adverse effects are nausea and vomiting that are usually easily controlled with standard antiemetic drugs, constipation, and some fatigue. The most serious and dose-limiting toxicity, observed in less than 10% of patients, is noncumulative myelosuppression, particularly thrombocytopenia occurring 3 to 4 weeks after treatment start,

TMZ is indicated for the treatment of patients with newly diagnosed glioblastoma multiforme concomitantly with radiotherapy and subsequently as monotherapy treatment. TMZ is also

indicated for treatment of malignant glioma, showing recurrence or progression after standard therapy. In the concomitant phase TMZ is administered orally at a dose of 75 mg/m^2 daily for 42 days concomitant with focal radiotherapy (60 Gy administered in 30 fractions) without dose reductions, but delay or discontinuation of TMZ can be considered weekly according to haematological and non-haematological side effect criteria. The TMZ is usually continued throughout the 42 day concomitant period (up to 49 days) in absence of adverse reaction.

Four weeks after completing the TMZ + Radiotherapy phase, TMZ is administered for up to 6 cycles of monotherapy treatment. The dose in cycle 1 (monotherapy) is 150 mg/m^2 once daily for 5 days followed by 23 days without treatment. At the start of Cycle 2, the dose is escalated to 200 mg/m^2 in absence of side effects.

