- resolution of rash  $\geq$  Grade 3 or diarrhoea  $\geq$  Grade 3 to Grade 2 or less
- resolution of any other Grade 3 or greater drug-related adverse reaction (either related to BIBW 2992 or to TMZ) to Grade 1 or baseline (whichever is higher).

If a patient develops side effect due to TMZ, recommendation for dose reduction and dose interruption should be followed as per the most up to date Summary of Product Characteristic (SPC) recommendation of the manufacturer.

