#### **4.2.3 Management of expected adverse events**

##### Management of diarrhoea

Close monitoring and proactive management of diarrhoea is essential for successful treatment of patients with BIBW 2992 and/or TMZ. Early and appropriate intervention can prevent the development of more severe diarrhoea. In most cases, loperamide controls diarrhoea caused by BIBW 2992 and/or TMZ.

Loperamide should be available at the start of therapy and kept with the patient at all times; it is therefore advisable that patients be given a prescription at the time of initiating study treatment.

The recommendations for management are as follows:

- If any diarrhoea is experienced (CTCAE Grade 1), two 2 mg loperamide tablets should be taken immediately, followed by one 2 mg tablet with every loose bowel movement, up to a maximum daily dose of 10 tablets (20 mg).
- Patients should be advised to avoid lactose-containing products or any foods known to aggravate diarrhoea.
- Oral hydration is essential regardless of severity; appropriate rehydration (1.5 litres/m^2/day plus equivalent of actual fluid loss) has to be ensured in the event of CTCAE Grade 2 and Grade 3 adverse reaction.
- For CTCAE Grade 3 diarrhoea lasting  $\geq 2$  days or CTCAE Grade 2 diarrhoea lasting  $\geq 5$  days despite adequate antidiarrhoeal treatment, BIBW 2992 and/or TMZ must be paused until recovery to CTCAE  $\leq$  Grade 1 or baseline in the individual treatment course. Upon recovery, BIBW 2992 and/or TMZ should be resumed at a reduced dose according to the dose reduction scheme outlined in Section 4.1.4.

The occurrence of diarrhoea and the outcome of treatment will be recorded in the AE section of the eCRF. Antidiarrhoeal treatments should be documented in the concomitant medication section of the eCRF.

If despite optimal supportive care and the treatment pause, diarrhoea does not resolve to CTCAE Grade  $\leq 1$  or baseline within 14 days, the patient must be removed from the study. Exception to this in patients who derive obvious clinical benefit according to the investigator's judgment could be considered upon discussion with BI's Clinical Monitor Local (CML).

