### Management of rash and acne

A proactive and early approach to management of rash is crucial. Rash can be managed by a variety of treatment options to relieve symptoms and improve the rash.

General/Prevention: strict sun protection; use of a sunscreen of SPF 15 or higher, preferably containing zinc oxide; use of a thick, alcohol-free emollient cream; avoid harsh detergents, avoid using a solarium.

- CTCAE Grade 1 rash: mild rash may not need treatment. However, if treatment is considered necessary, topical hydrocortisone (1% or 2.5%) cream and/or clindamycin 1% gel can be used.
- CTCAE Grade 2 rash: relief from major symptoms caused by CTCAE Grade 2 skin adverse reaction should be achieved by a combination of local and systemic therapies including:
  - 1) Systemic antibiotics (doxycycline or minocycline etc.)
  - 2) Topical treatment (hydrocortisone 2.5% cream, clindamycin 1% gel, pimecrolimus 1% cream) and/or antihistamines (diphenhydramine, etc.)
  - 3) Oral prednisone (short term i.e.<14 days treatment) may be added at investigator's discretion.

Systemic and topical treatment should be initiated at the start of CTCAE Grade 2 rash and continue until improvement or resolution to CTCAE Grade  $\leq$  1 or baseline.

- CTCAE Grade 3 (or greater) rash: may be treated in a manner similar to CTCAE Grade 2 rash. However, if CTCAE Grade  $\geq$  3 rash persists despite optimal supportive care (including systemic antibiotics), treatment with BIBW 2992 and/or TMZ should be discontinued until recovery to  $\leq$  CTCAE Grade 1 rash or baseline CTCAE Grade (whichever is higher).

Thereafter patients can resume BIBW 2992 treatment at the next lower dose level as outlined in Section 4.1.4. If CTCAE Grade $\geq$ 3 rash does not resolve to CTCAE Grade $\leq$ 1 or baseline within 14 days after stopping BIBW 2992 and/or TMZ treatment and despite optimal supportive care, the patient will be taken off drug and off protocol. Exception to this in patients who derive obvious clinical benefit according to the investigator's judgment could be considered upon agreement with BI's Trial Clinical Monitor (TCM).

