A3.6	Requirement for treatment with P-gp inhibitors or P-gp inducers	For patients enrolled after implementation of CTP amendment 2 only: Exclusion criteria EX23 is met.
B	Informed consent	
B1	Informed consent not given	
B1.1	Informed consent 1 not given	For patients enrolled before implementation of CTP amendment 3 and who do not already have an MGMT test result only: Inclusion criteria IN7 is not met. or Date of informed consent 1 is missing.
B1.2	Informed consent 2/3 not given	Inclusion criteria IN7 is not met. or Date of informed consent 2/3 is missing.
B2	Informed consent given too late	
B2.1	Informed consent 1 given too late	For patients enrolled before implementation of CTP amendment 3 and who do not already have an MGMT test result only: Date of any study specific procedures before date of informed consent 1.
B2.2	Informed consent 2/3 given too late	Date of any study specific procedures before date of informed consent 2/3.
C	Trial medication and randomisation	
C1	Incorrect trial medication taken	
C1.1	Incorrect TMZ dosing during concomitant treatment period (Regimen M only)	For patients in Regimen M only: At least one TMZ dose during concomitant treatment period not according to the dose described in Section 4.1.4.2 of the CTP.
C2	Treatment group assignment not followed	
C2.1	Afatinib treatment during concomitant treatment period in discordance with treatment group assignment	Initial dose of afatinib does not correspond to treatment group assignment. or Afatinib dose changes during concomitant treatment period not according to the dose reduction scheme described in Section 4.1.4.1.2 of the CTP.
C2.2	TMZ treatment during concomitant treatment period in discordance with treatment group assignment	For patients in Regimen M only: No dose of TMZ during concomitant period. or For patients in Regimen U only: At least one dose of TMZ during concomitant treatment period.
C3	Non-compliance	
C3.1	Afatinib non-compliance during concomitant treatment period	Total number of doses of afatinib missed for reasons other than AE is more than 8 during concomitant treatment period. or Number of consecutive doses of afatinib missed for non-AE reasons is more than 5 during concomitant treatment period.

[figure not shown]
Table 6.2: 1 Important Protocol Violations (continued)

Category / Code	Description	Comment/Example

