C3.2	TMZ non-compliance during concomitant treatment period (Regimen M only)	For patients in Regimen M only: Total number of doses of TMZ missed for reasons other than AE is more than 8 during concomitant treatment period.
C4	Trial specific PVs related to trial medication	
C4.1	Dose reduction scheme for afatinib not followed	Regardless of treatment period, incidence of DLT without subsequent adherence to the dose reduction scheme described in Section 4.1.4.1.2 of the CTP.
C4.2	TMZ treatment continued but re-treatment criteria not met (Regimen M only)	For patients in Regimen M only: Following the concomitant treatment period, TMZ not terminated despite re-treatment criteria described in Section 4.1.4.2 of CTP not met.
D	Concomitant medication	
D1	Prohibited concomitant medication	
D1.1	Prohibited medication use before the start of study treatment period	Inclusion criteria IN6 is not met. or At least one of exclusion criteria EX1-EX5 is met. or Prohibited concomitant therapy use before start of study treatment (defined in Sections 3.3.1 and 3.3.2 of the CTP).
D1.2	Prohibited medication use during study treatment period	Prohibited concomitant therapy use during study treatment (defined in Section 4.2.2 of the CTP).
D2	Mandatory medication not taken	
D2.1	Incorrect dose of radiotherapy administered during the concomitant treatment period	Radiotherapy total dose not equal to 60 Gy.
D2.2	Pneumocystis pneumonia prophylaxis not taken during concomitant treatment period (Regimen M only)	For patients in Regimen M only: Concomitant therapy use during concomitant treatment period does not include appropriate prophylaxis.
G	Trial specific protocol violations	
G1	Non-adherence to safety withdrawal criteria	Trial medication continued despite withdrawal criteria in Section 6.3 of the CTP met.
G2	Other protocol violations affecting patient rights or safety	Any other protocol violation that affects the rights or safety of trial patients.

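### Protocol Sections 4.1.4.2 and 4.2.3 conflict on restarting temozolomide at Grade 2 diarrhoea or rash in maintenance, the dose at restart has no clear source, and two SAP violation codes inherit the ambiguity

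*Protocol*

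**What the plan says.** **Grade at restart.** The TMZ re-treatment criteria in protocol Section 4.1.4.2 cover the maintenance courses that follow radiotherapy (RT) and the four-week TMZ break. For rash or diarrhoea of Grade 3 or worse, they ask for resolution from "Grade 3 to Grade 2 or less". Any other drug-related reaction of Grade 3 or worse must return to Grade 1 or baseline.

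Section 4.2.3 sets its own rule for the same two events. For diarrhoea that meets its duration triggers, BIBW 2992 and/or TMZ stay paused until at most "Grade 1 or baseline in the individual treatment course". For Grade 3 or worse rash that persists despite optimal care, "treatment with BIBW 2992 and/or TMZ should be discontinued until recovery to" Grade 1 or lower, or baseline. In both parts, a patient who does not recover to that level within 14 days is removed, unless the clinical-benefit exception is agreed.

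**Dose at restart.** The diarrhoea part of 4.2.3 says "Upon recovery, BIBW 2992 and/or TMZ should be resumed at a reduced dose according to the dose reduction scheme outlined in Section 4.1.4". Table 4.1.4.1.2: 1, the only reduction table in Section 4.1.4, lists BIBW 2992 doses in mg. For side effects due to TMZ, Section 4.1.4.2 says that the "recommendation for dose reduction and dose interruption should be followed as per the most up to date Summary of Product Characteristic".

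**SAP.** Table 6.2: 1 defines important protocol violation C1.1 for Regimen M as "At least one TMZ dose during concomitant treatment period not according to the dose described in Section 4.1.4.2 of the CTP". Code C4.2 applies after the concomitant period and is triggered by "TMZ not terminated despite re-treatment criteria described in Section 4.1.4.2 of CTP not met". Neither code cites Section 4.2.3.

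**The concern.** Two operative dosing rules give different answers for the same patient. In maintenance, a patient whose Grade 3 diarrhoea has settled to Grade 2 by the next cycle meets the listed re-treatment criterion in one section. In the other section the same patient must be held, and may have to leave the study. Nothing says which section takes precedence.

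The dose question adds to this. A site told to resume TMZ at a reduced dose finds no TMZ scheme at the place cited, only a pointer to an external label.

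At stake are consistent handling of patients between sites, and violation listings that mean the same thing whichever section a site read. Section 3.2 also describes the TMZ background in Regimen M as a standard fixed dose, so the protocol should say plainly whether TMZ may be reduced during RT.

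**Working it through.** The plan states no figure on this point, so the check sets the rules side by side.

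**1. Restart grade.** Take a Regimen M patient in maintenance with baseline Grade 0 or 1. Diarrhoea or rash reached Grade 3, the 4.2.3 trigger was met, and TMZ was paused.

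| Grade on the planned restart day | 4.1.4.2 listed criterion | 4.2.3 | Same answer? |
|---|---|---|---|
| 0 or 1 | allows TMZ | allows TMZ | yes |
| 2 | allows TMZ | holds TMZ; removal if not recovered within 14 days, unless excepted | no |
| 3 or more | does not allow | does not allow | yes |

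The conflict sits at Grade 2 alone. If baseline were Grade 2, both rules would allow the restart. For nausea and vomiting the two sections agree on Grade 1 or baseline after a Grade 3 event. Section 4.2.3 also pauses for Grade 2 diarrhoea lasting five days or more despite treatment. The listed criteria in 4.1.4.2 do not address that case, which is a gap rather than a contradiction.

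**2. Restart dose.** The three parts of 4.2.3 treat TMZ differently.

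| Part of 4.2.3 | Paused | Reduced at restart | Source cited |
|---|---|---|---|
| Diarrhoea | BIBW 2992 and/or TMZ | BIBW 2992 and/or TMZ | a scheme in Section 4.1.4 |
| Nausea and vomiting | BIBW 2992 and/or TMZ | BIBW 2992 only | Table 4.1.4.1.2: 1 |
| Rash | BIBW 2992 and/or TMZ | BIBW 2992 only | Section 4.1.4 |

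Only the diarrhoea part calls for a TMZ reduction, and it does not say how far or in which phase.

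**3. SAP codes, applied to what a site might do.**

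- Restart TMZ at Grade 1 or lower, as 4.2.3 asks: this always satisfies the looser Grade 2 criterion, so C4.2 cannot be triggered on grade.
- Reduce TMZ during RT under 4.2.3: C1.1 is triggered if the dose described in 4.1.4.2 means 75 mg/m² alone. It arguably is not if that description includes the SPC sentence in the same section.
- Reduce TMZ in maintenance: this is outside C1.1, which is limited to the concomitant period, and outside C4.2, which tests criteria and not dose.
- Reduce BIBW 2992 alone, which the and/or wording permits: no TMZ code applies.
- Restart TMZ at Grade 2 in maintenance, against 4.2.3: the listed 4.1.4.2 grade criterion is met, so C4.2 does not catch it. No code tests the 4.2.3 grade. The catch-all G2 might be used by judgement. G1 tests the Section 6.3 withdrawal criteria, so it would overlap only where the event was a DLT still unrecovered 14 days after the last dose.

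**4. Size.** Section 1.2.1 gives Grade 3 diarrhoea in 22.4% of patients in Phase II monotherapy trials started at 50 mg. Applied to the ceiling of 30 patients per regimen, 0.224 × 30 = 6.7. Applied to the Section 7.6 scenario of 12 + 6 + 6 = 24 per regimen, 0.224 × 24 = 5.4. These are counts of Grade 3 diarrhoea, not of the conflict. The conflict also needs the duration trigger, TMZ itself paused, maintenance TMZ still under way, and exactly Grade 2 on the restart day. The documents give no rate for any of these, and none for Grade 3 rash.

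**The case against.** The strongest reply is that the conflict is narrow and partly answered by the cross-references. The two sections have different triggers: a Grade 3 event that settles before the 4.2.3 trigger is met falls under 4.1.4.2 alone. The and/or wording lets a site pause BIBW 2992 only. A site can satisfy both grade rules by waiting for Grade 1. The diarrhoea part cites Section 4.1.4 as a whole, which contains 4.1.4.2 and its SPC sentence, so a TMZ source exists. Section 4.1.4.2 also adds its criteria to those of the TMZ package insert, which is not available here and might be stricter.

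Most of this stands as a limit on scope, and it does not remove the conflict. Nothing tells a site to wait, and 4.1.4.2 separates rash and diarrhoea from all other reactions, so its Grade 2 threshold looks deliberate. The SPC sentence covers side effects due to TMZ and leaves open whether to reduce at all, whereas the diarrhoea part calls for a reduction.

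Four stronger readings are tempting, and the documents do not support them.

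- A reader might infer that the SAP would code any site following 4.2.3 as a violator. On grade it cannot. On dose it could do so only for a TMZ reduction during RT, and only on the narrow reading of C1.1. Violations are described for patients, not sites.
- A reader might infer that the MTD is distorted. The grade conflict arises only in maintenance, while the MTD rests on DLTs in the 42-day RT period. SAP Section 6.2 defines no per-protocol set and only describes violations.
- A reader might take the Grade 3 diarrhoea rate as the frequency of the conflict. It is not, as shown in the check.
- A reader might treat Section 1.2.2, which describes TMZ during RT as given "without dose reductions, but delay or discontinuation of TMZ can be considered weekly", as a trial rule. It is background on usual administration and shows only why the point needs stating.

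**Conclusion.** The concern holds in a limited form. In Regimen M maintenance, 4.1.4.2 and 4.2.3 conflict at exactly Grade 2 diarrhoea or rash, provided the 4.2.3 trigger has been met, TMZ has been paused, and baseline is Grade 1 or lower. Separately, the diarrhoea part of 4.2.3 directs a reduced dose of BIBW 2992 and/or TMZ to a scheme that is tabulated only for BIBW 2992.

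The SAP consequence is one possible false flag (C1.1, during RT, narrow reading) and one likely miss (C4.2, Grade 2 restart). The primary DLT/MTD analysis set is unaffected.

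The number of patients concerned cannot be derived from the documents. For diarrhoea, about 5 to 7 Regimen M patients is at most a loose upper bound, and only if the 50 mg monotherapy rate carries over to this trial. The change is worth making because it bears on patient safety and consistent conduct.

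**What to change.** 1. Reconcile Sections 4.1.4.2 and 4.2.3 so that a single TMZ restart rule applies to diarrhoea and a single one to rash, including the 14-day consequence. Which rule that should be is for the sponsor's clinical team.
2. In each part of 4.2.3, replace the and/or wording with separate statements for BIBW 2992 and TMZ. Each should name the source of any dose reduction and say whether it applies during RT, in maintenance, or both.
3. In SAP Table 6.2: 1, align C1.1 so that a TMZ change directed by the protocol is not coded as a violation. Align C4.2 so that a restart outside the reconciled rule is caught.

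The cost is wording in two protocol sections and two SAP table rows, with no extra patients, visits or procedures. The protocol change is not purely administrative, so under Section 8.5 it would go to the ethics committee and the competent authority.

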##### **4.1.4.1.1 Dose escalation scheme for BIBW**

Initially, 3 evaluable patients will be treated per dose level. As soon as one patient experiences a DLT (see section 5.2.3), 3 new patients will be treated at that dose level, to treat a minimum of 6 evaluable patients. If no other patients experience DLT the dose will be escalated to the next level and 3 further patients treated. If two or more of six patients

experience DLT, three additional patients will be treated at one dose tier below unless six have already been treated at that dose tier.

The MTD (see section 5.2.4) is the highest dose at which no more than one of 6 patients experiences DLT. Once the MTD is determined, patient enrolment at higher dose tiers will be suspended.

The MTD cohort in each Regimen may be expanded to include up to 12 patients.

Intra-patient dose escalation will not be permitted.

The first three patients at each dose level will be treated and observed for at least 6 weeks (42 days) during RT before the next cohort of new patients are treated at the next higher dose level (Table 4.1.4.1.1: 2 and 4.1.4.1.1: 3).

Table 4.1.4.1.1: 1 Rules for dose escalation for regimen M and U

Number of Patients with DLT at a Given Dose Level	Escalation Decision Rule
0 out of 3	Enter 3 patients at the next dose level.
1 out of 3	Enter at least 3 more patients at this dose level. - If 0 of these 3 patients experience DLT, proceed to the next dose level. - If 1 or more of this group suffer DLT, then dose escalation is stopped. Three (3) additional patients will be entered at the next lower dose level if only 3 patients were treated previously at that dose.
$\geq 2$ out of 3	Dose escalation will be stopped. Three (3) additional patients will be entered at the next lower dose level if only 3 patients were treated previously at that dose.

The decision regarding dose escalation steps will only be made after agreement with the sponsor's Trial Clinical Monitor (TCM).

Dose escalation and entry of patients into the next dose cohort will begin only after accrual of the required minimum number of patients has been achieved and all patients in the cohort are considered following completion of 6 weeks BIBW2992 treatment ((42 days ) during RT). Patients who are not treated until the end of these 6 weeks for any reasons other than DLT will be replaced (section 6.3.1).

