### 4.1.4.1.2 Dose reduction scheme for BIBW: Regimen U and M

If a patient develops side effect that meets criteria for DLT (for definition refer to Section 5.2.3) regardless of treatment cycle, treatment with BIBW 2992 must be paused. If all drug-related adverse events recover to CTCAE Grade 1 or baseline (whichever is higher) within 14 days of stopping treatment with BIBW 2992, treatment may be resumed with dose reductions according to Table 4.1.4.1.2: 1. Otherwise, the patient will be taken off study. Exceptions to this are patients who derive obvious clinical benefit according to the investigator's judgment. These patients could be considered in agreement with BI's Trial Clinical Monitor (TCM) for further treatment.

If a patient need to dose reduced BIBW 2992 during RT, the dose of BIBW 2992 during the maintenance period will need to be discussed and decided on a case to case base between BI Trial Clinical Monitor and the investigator at site (keep BIBW2992 reduced daily dose or change as planned for 40mg BIBW2992 daily)

Table 4.1.4.1.2: 1 Dose reduction scheme for Regimen M and U

Treatment prior to treatment pause and dose reduction BIBW (mg)	Dose reduction		
	1 st DLT BIBW (mg)	2 nd DLT BIBW (mg)	3 rd DLT
20	Off-study		
30	20	Off-study	
40	30	20	Off-study

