#### Management of nausea and vomiting

Nausea and vomiting may significantly affect patients' adherence to the treatment and their quality of life. In order to reduce the occurrence and the intensity of emesis, the patients should be treated according to the recommendation given in Table 4.2.3: 1.

Table 4.2.3: 1 Management of nausea and vomiting

CTCAE Grade	Antiemetic treatment
Nausea = grade 1 and Vomiting = grade 0	No antiemetic treatment unless judged necessary by investigator
Nausea = grade 2 and Vomiting = grade 0	Antiemetic treatment   Pause BIBW 2992 and/or TMZ treatment if grade 2 vomiting or grade 2 nausea persist for 7 or more consecutive days despite optimal supportive care. Resume treatment when CTCAE grade $\leq 1$ .
Nausea = grade 0, 1 or 2 and Vomiting = grade 1 or 2	Antiemetic treatment 
Vomiting $\geq$ grade 3 or Nausea $\geq$ grade 3	Pause BIBW 2992 and/or TMZ treatment

	until return to CTCAE grade $\leq$ 1 or baseline  .
--	-----------------------------------------------------------------

1 Antiemetic treatment should follow the recommendations given in the Consensus Statement of the Antiemetic Subcommittee of the Multinational Association of Supportive Care in cancer (MASCC): Prevention of chemotherapy- and radiotherapy-induced emesis: Results of the Perugia Consensus Conference (R06-0986).

2 Baseline is defined as the CTCAE grade at the start of treatment.

After a treatment pause the dose of BIBW 2992 should be reduced according to the dose reduction scheme in Table 4.1.4.1.2: 1. The occurrence of nausea and/or vomiting and the outcome of treatment will be recorded in the AE section of the eCRF. Antiemetic treatments should be documented in the concomitant medication section of the eCRF with the start and end of treatment dates and daily dose. In case of nausea and/or vomiting  $\geq$  CTCAE grade 2, appropriate hydration (1.5 L/m^2/day plus hydration deficit) must be ensured.

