#### b) Non-hematologic adverse reaction:

1. CTCAEv3 Grade  $\geq 3$  nausea or vomiting is occurring despite appropriate use of standard anti-emetics for at least three days.
2. CTCAEv3 Grade  $\geq 3$  diarrhoea despite appropriate use of standard anti-diarrheal therapy for at least three days.
3. CTCAEv3 Grade  $\geq 3$  rash despite standard medical management as outlined in Section 4.2.3 and lasting  $>7$  days.
4. CTCAEv3 Grade  $\geq 2$  cardiac left ventricular function.
5. CTCAEv3 Grade  $\geq 2$  worsening of renal function as measured by serum creatinine, newly developed proteinuria, or newly developed decrease in glomerular filtration rate.
6. All other non-hematological toxicities of CTCAEv3 Grade  $\geq 3$

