### **6.3.1 Replacement of patients**

Patients who do not receive study treatment during the chemoradiation phase for more than 5 consecutive days or more than 8 non-consecutive days for any reasons other than DLT will be replaced.

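### Patients whose treatment is ended or long interrupted by sub-DLT BIBW 2992 toxicity are replaced, so they drop out of the escalation and MTD count at every dose level

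*Protocol*

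**What the plan says.** **Escalation and MTD.** Under Protocol 4.1.4.1.1 a dose clears with 0 DLTs in 3 patients or 1 in 6. Section 5.2.4 sets the MTD at no more than 1 DLT in 6 (17%). Only DLTs enter either rule. The step after 20 mg is 40 mg; 30 mg is an option only if 40 mg fails.

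**Replacement.** Section 4.1.4.1.1: "Patients who are not treated until the end of these 6 weeks for any reasons other than DLT will be replaced (section 6.3.1"). Section 6.3.1 also replaces "Patients who do not receive study treatment during the chemoradiation phase for more than 5 consecutive days or more than 8 non-consecutive days", again excepting only DLT.

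**DLT threshold (5.2.3).** Gastrointestinal events need Grade 3 or worse "diarrhoea despite appropriate use of standard anti-diarrheal therapy for at least three days", or Grade 3 or worse "nausea or vomiting is occurring despite appropriate use of standard anti-emetics for at least three days". Left ventricular and renal events count from Grade 2, and all other non-haematological toxicities from Grade 3.

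**Pauses and removals below that threshold.** Section 4.2.3 requires a pause for Grade 2 diarrhoea of 5 days or more, and for Grade 2 nausea or vomiting of 7 days or more. Diarrhoea not resolved within 14 days of the pause takes the patient off study, with an exception for clinical benefit. Section 4.2.1 requires permanent discontinuation for interstitial lung disease, whatever the grade.

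**After a pause.** For diarrhoea: "Upon recovery, BIBW 2992 and/or TMZ should be resumed at a reduced dose according to the dose reduction scheme outlined in Section 4.1.4". For nausea and vomiting: "After a treatment pause the dose of BIBW 2992 should be reduced according to the dose reduction scheme in Table 4.1.4.1.2: 1". For rash the wording is weaker: "Thereafter patients can resume BIBW 2992 treatment at the next lower dose level as outlined in Section 4.1.4". The row header of Table 4.1.4.1.2: 1 begins "Treatment prior to treatment pause and dose reduction", but its columns are headed first, second and third DLT. At 20 mg its only entry is off-study.

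**SAP.** The primary endpoint (5.1) is an investigator-defined DLT with onset in the 42-day period. The treated set is used for every analysis (6.3). Violation code C3.1 applies the same 5- and 8-dose limits but ignores doses missed because of an adverse event.

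**The concern.** Replacement is harmless when the reason for stopping is unrelated to the drug. Here the only reason exempted is a DLT, so a patient who cannot continue because of a lesser but drug-related toxicity is handled like one who moved away. That is informative exclusion from the primary endpoint: patients who tolerated the dose poorly leave both numerator and denominator, and a fresh patient takes the place.

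The MTD is the only primary endpoint, and clearing 20 mg doubles the dose. Diarrhoea, nausea and vomiting are among the most frequent drug-related events that Protocol 1.2.1 lists for BIBW 2992, so the affected toxicities are not remote ones.

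**Working it through.** **Step 1. Does a sub-DLT route out of the count exist on firm text?** Three routes need no interpretation of the dose-reduction table:
- Grade 2 diarrhoea, paused and not resolved within 14 days: off study under 4.2.3. It is not a DLT, because criterion 2 of 5.2.3 starts at Grade 3.
- Interstitial lung disease below Grade 3: drug stopped for good under 4.2.1. It is not a DLT, because the catch-all criterion starts at Grade 3.
- Any related sub-DLT pause of more than 5 consecutive days: replaced under 6.3.1 at 20, 30 or 40 mg. This takes a BIBW 2992 pause as not receiving study treatment, which is plain in Regimen U. Regimen M is less explicit about a pause of one of the two drugs.

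**Step 2. The plan's own figure.** 1/6 = 16.7%, which matches the stated 17%.

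**Step 3. What the rules do with such patients.**
- Six treated, three removed for sub-DLT toxicity, three finish without DLT: the rule reads 0/3 and escalates, although 3/6 = 50% stopped for toxicity.
- Eight treated, one DLT, two such removals: 1/6 = 17% among evaluable patients, which meets the MTD rule; 1/8 = 12.5% in the SAP treated set; (1 + 2)/8 = 37.5% if the removals count.

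**Step 4. Chance of clearing 20 mg.** Let d be the DLT risk and t the risk of sub-DLT removal, as mutually exclusive outcomes with independent patients. The documents give neither at 20 mg, so both are assumptions. For an effective per-patient risk p,

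P(clear) = (1−p)³ + 3p(1−p)² × (1−p)³.

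With replacement p = d/(1−t). If removals count, p = d + t.

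At d = t = 10%:
- Replacement: p = 0.10/0.90 = 0.111, giving 0.702 + 0.185 = 0.887.
- Counted: p = 0.20, giving 0.512 + 0.197 = 0.709.

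| d | t | Replaced | Counted | Gap (points) |
|---|---|---|---|---|
| 5% | 5% | 97.1% | 90.6% | 6.5 |
| 5% | 10% | 96.8% | 81.4% | 15.4 |
| 5% | 20% | 96.0% | 60.0% | 36.0 |
| 10% | 5% | 89.7% | 81.4% | 8.3 |
| 10% | 10% | 88.7% | 70.9% | 17.8 |
| 10% | 20% | 86.2% | 49.4% | 36.8 |
| 15% | 5% | 79.8% | 70.9% | 8.9 |
| 15% | 10% | 78.0% | 60.0% | 18.0 |
| 15% | 20% | 73.6% | 39.6% | 34.0 |

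**Step 5. Would barring replacement be enough?** No. If removed patients are kept as DLT-free, p = d, and at d = 10% the dose clears 90.6% of the time, slightly more often than the 88.7% under replacement at t = 10%. The count has to change as well.

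**The case against.** The strongest objection concerns 20 mg. A reader might infer that every sub-DLT pause at the starting dose ends off-study. The documents do not say so. Section 4.1.4.1.2 limits the scheme to events meeting the DLT criteria, and the off-study entry sits under the first-DLT column. The nausea table tells sites to resume once Grade 2 symptoms settle to Grade 1, and the withdrawal list in 6.3 does not name a first, recovered sub-DLT event. In Regimen M, TMZ alone may be paused. This stands: off-study after such a pause is an inference. It is not an idle one, since 4.2.3 itself sends Grade 2 nausea to that table and asks for a dose that does not exist.

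Second, the Grade 3 gap is narrower than it looks. The three days in the DLT criteria can be read as duration of supportive therapy, and loperamide starts at Grade 1, so Grade 3 diarrhoea paused at day 2 may already qualify. This also stands, and the firm routes above do not use it.

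Third, where to set the DLT threshold is the sponsor's choice. True, but choosing not to count an event differs from removing the patient who had it.

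Fourth, the events are not hidden. The Trial Clinical Monitor must agree each escalation, SAP 7.8.1 tabulates non-serious events leading to discontinuation or reduction, and Protocol 7.1 rests the dose choice on more than DLTs. These are real safeguards, but no rule makes any of them count.

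Fifth, no document supports a removal risk of 5–20%. Protocol 4.1.3 calls 20 mg tolerable with chemotherapy, and 1.2.1 gives a monotherapy MTD of 50 mg. The upper end of the range may be unrealistic.

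**Conclusion.** The counting gap is real and applies at every dose level: sub-DLT, BIBW 2992-related toxicity that ends or long interrupts treatment in the radiotherapy phase is removed from the rules that set the primary endpoint, and the SAP shows the same patients as DLT-free.

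Two stronger readings do not hold. It is not true that treatment-ending toxicity at 20 mg never counts: DLT-grade toxicity there also ends treatment and is counted. Nor is the replacement problem confined to 20 mg; only the missing lower dose is.

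The structural conclusion rests on the text. The size rests on assumed rates: an 18-point difference in the chance of clearing 20 mg at d = t = 10%, 6 to 9 points at t = 5%, and 34 to 37 at t = 20%. These figures compare two ways of counting; they do not show an arithmetical error in the plan. The change is cheap and should be made, but the documents do not show that the MTD would in fact be wrong.

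**What to change.** 1. **Section 5.2.3.** Add: *For escalation and MTD, a BIBW 2992-related event with onset in the radiotherapy phase that leads to permanent discontinuation of BIBW 2992, or does not recover within the 14-day pause window, counts as a DLT.*
2. **Sections 4.1.4.1.1 and 6.3.1.** Limit replacement to reasons other than a BIBW 2992-related adverse event. This brings the protocol closer to SAP C3.1, which already sets aside doses missed for an adverse event. It must go together with change 1.
3. **Section 4.2.3.** State the action at 20 mg: resumption at 20 mg after a first recovered sub-DLT pause, with the patient kept in the count.

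Whether shorter, recovered related pauses should also count as DLTs is for the sponsor. Making every pause of more than 5 days dose-limiting would be hard to square with the 14 days that 4.1.4.1.2 allows for recovery from a DLT.

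Cost: three short text changes, no new visits or data items, and fewer replacements (six evaluable patients otherwise need on average 6/0.9 = 6.7 enrolled at t = 10%, or 6/0.8 = 7.5 at t = 20%). A 14-day window that opens after day 28 runs past day 42, so an occasional escalation decision would wait for it. Escalation would stop more often if sub-DLT toxicity is common (20 mg clears 71% instead of 89% of the time at the assumed 10% rates). No tier lies below 20 mg, so failing there would leave that regimen without an MTD.
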